[name], ABPP

Professor
Florida International University
[name]
[name]
[contact]
[contact]

July 16th, 2025

To whom it may concern,

The following study protocol and statistical analysis plan are submitted in reference to NCT03643848 for R01MH116005, Sleep-dependent Negative Overgeneralization in Peripubertal Anxiety.

Aim 3 of this grant was considered a clinical trial at the time it was funded due to random assignment and experimental manipulation. Aims 1 and 2 of the grant were observational and were not considered a clinical trial. The protocol and analytic plan presented here are therefore focused on Aim 3. The primary outcomes for the clinical trial included memory outcomes at 1 week and 12 hours, as detailed in clinicaltrials.gov and the analytic plan. Individual data from the trial and the rest of the project are available via NIMH Data Archive.

Sincerely,

A handwritten signature in black ink, appearing to read '[name]'.

[name], ABPP (PI; contact)

Protocol (Aim 3 of R01MH116005)

Objectives.

Our primary objective is to test the malleability of memory processing during sleep in anxious youth. Specifically, we aim to override the selective replay of negative memories during sleep through competitive displacement, utilizing cued audio reactivation of neutral stimuli relative to sham cueing during NREM sleep. We anticipate this will reduce negative overgeneralization in peri-pubertal youth with clinical anxiety.

Design.

We will conduct a double-blind randomized design to examine the effects of Targeted Memory Reactivation (TMR) relative to Sham during NREM sleep on negative overgeneralization in youth with anxiety. Sixty youth diagnosed with Social, Separation, and/or Generalized Anxiety Disorder will first undergo clinical assessment and a 7-10 day baseline evaluation of sleep patterns. Participants will then complete an encoding session (referred to as the 'Study' session) in an MRI scanner. Subsequently, they will travel to the sleep lab at Nicklaus Children's Hospital for polysomnography (PSG) hook-up. Following PSG setup, participants will be randomly assigned to either the TMR (n=30) or sham reactivation (n=30) group by an independent research assistant operating from a control room. To maintain double-blinding, participants and the research assistant directly interacting with them will remain unaware of group assignment for the duration of the study. During PSG-monitored NREM sleep, previously-paired neutral sounds from the encoding session will be replayed in the TMR group. In contrast, for the sham group, guitar strums will be played during NREM sleep. Memory outcomes will be assessed at two post-sleep time points: an initial behavioral assessment approximately 11-12.5 hours after the encoding session, and a final assessment approximately 1 week later (between 11 am and 3 pm) conducted in the MRI. More detailed methods for each of these sessions are provided below. Analyses will compare the effects of neutral TMR (relative to sham) on negative and neutral generalization at both the 12-hour and 1-week delay assessment points.

Methods .

Participants. A total of 60 children between the ages of 10 and 13 years will participate in Aim 3, beginning in the 4th year of the broader project period. Participants will be recruited from specialty child mental health clinics at FIU and Nicklaus Children's Hospital as well as via community advertisements.

The 10-13 year age range is aligned with peri-puberty and allows for the study of sleep-dependent mechanisms of overgeneralization prior to the steep escalation of emotion-related disorders through mid-late adolescence (peaking from 16-18 years). In line with the RDoC framework, we will sample across a continuum of anxiety severity to capture variability on emotion reactivity and sleep neurophysiology during this sensitive period of development, while minimizing developmental variability in the sample. We will focus on symptoms of Separation Anxiety Disorder (SAD), Social Phobia (SP), and Generalized Anxiety Disorder (GAD) based on phenotypic overlap in emotion responding and sleep across these diagnostic categories and comorbidities. The proposed framework has implications for other disorders characterized by

negative emotions and sleep disruptions, such as OCD and Panic Disorder. Given high comorbidity with GAD, SAD, and SP, we do allow for elevated symptoms in these diagnostic categories. However, we exclude those who meet full diagnostic criteria for these disorders because they show somewhat less phenotypic overlap with SAD, GAD and SP in sleep and emotion response profiles and it is important to balance generalizability of findings with precision of investigation at this stage of inquiry. Extensive efforts will be made to prevent attrition and optimize parent and child participation. Parents of children will be compensated up to \$300 for completion of the study.

Intake, Screening and Baseline Characteristics. Following a brief phone screen to verify potential inclusion (e.g. no braces, within age range etc.) eligible families will be scheduled for consent and assessment to verify group inclusion/exclusion criteria. Inclusion and exclusion criteria are detailed further in clinicaltrials.gov entry.

After informed parental consent and child assent/consent, the *Anxiety Disorders Interview Schedule Child/Parent versions* (ADIS C/P) will be administered by a trained clinician to assess for past and current anxiety diagnoses, and to screen for other psychiatric diagnoses. The *Pediatric Anxiety Rating Scale* (PARS) will be administered by a trained clinician to capture the severity of anxious symptomatology. Youth and parents will also complete symptom severity inventories for anxiety: *Screen for Child Anxiety Related Emotional Disorders* (SCARED) a 41-item child and parent self-report to assess severity of symptoms of separation anxiety, social phobia, general anxiety disorders and panic disorder. These measures will be included in a factor analysis to generate a factor score that can be used for primary analyses (anxiety severity factor). General intelligence will be measured by the *Wechsler Abbreviated Scale of Intelligence* (WASI), significant memory impairments will be assessed using the *Auditory Verbal Learning Test*, sleep-related disorders (e.g. sleep apnea, parasomnias) will be evaluated by *Structured Clinical Interview of Sleep Disorders*, an inventory of habitual sleep-wake times will be measured by *Pittsburgh Sleep Quality Index*, and a history of chronic (>6 months) or current medication that impacts emotion and sleep-wake function (i.e. steroids, psychotropics) will be gathered in a brief interview. At the end of the intake visit, eligible participants will take home an actigraph and sleep diary to assess sleep for 7-10 days prior to the memory task procedures. This assessment is conducted in order to 1) capture a representative, prospective sampling of habitual sleep/wake patterns in the home environment and 2) to use sleep data to ensure the lab protocol is aligned with sleep timing at home (within 3 hours of bedtime/wake time). The use of the internet version of the Pittsburgh Sleep Diary, modified for use with children and adolescents, allows for verification that data is collected within close temporal proximity to sleep. Actigraphy will quantify the level and pattern of activity across the 24-hour period to approximate sleep patterns in correspondence with the sleep diary. The wristwatch-sized device (Actiwatch-2, Philips Respironics) is worn on the non-dominant arm, and records number of movements per minute. It summarizes the frequency of motions into epochs of specified time duration and can later be analyzed to generate various sleep parameters.

Emotional Memory Task Protocol. As in past studies and our preliminary data, negative overgeneralization will be assessed by the administration of an emotional memory task that lasts approximately ~20 minutes (two ~10-minute runs) during the Study session and ~40 minutes (four ~10-minute runs) during Test sessions. BOLD fMRI data will be collected during the Study session and at the Test session following a 1-week delay. During the task, images (negative, neutral) are presented in the center of the screen on a black background for 2.5 seconds. Simultaneously, semantically related auditory cues will be presented and co-terminate with the visual stimulus. A variable duration (4-9 seconds) fixation cross is displayed in the center of the screen on a black background during the inter-trial-interval. During the Study session participants will undergo an incidental encoding task where they are shown images in a randomized order and asked to rate the images for their emotional valence (negative, neutral). Test sessions follow at both a 12-hour delay and 1-week delay. During the Test sessions, participants will see session specific stimuli that were presented to them during the encoding phase (targets), new stimuli (foils), and stimuli that are similar to the ones seen at encoding but not identical (lures). Emotional valence and similarity level will be evenly distributed across the targets, lures, and foils. Participants will be asked to indicate whether the image they are currently viewing is “old” or “new” with a button press. Instructions during the retrieval phase will explicitly indicate that only the exact image that was presented during the Study phase can be called “old.” Thus, responding to critical lures (“false alarms”) will provide a signature of generalization within each participant. A total of 175 images will be presented during the Study phase and 266 images will be presented during the Test phases. Sixteen (8 neg) of the original 175 images presented during the Study phase will be tested at the 12-hour Test session along with 30 lures (15 neg) and 24 foils (12 neg); 44 study images (22 neg) will be tested at the 1-week Test session with 85 lures (43 neg) and 67 foils (31 neg).

Sleep Experimental Protocol. For participants randomized to the TMR condition auditory cues that were previously paired with neutral images during Study will be presented during NREM sleep. In contrast, sham auditory stimuli – random guitar strums – will be presented during NREM sleep to participants randomized to the sham group. Specifically, during post study session periods of NREM sleep, sounds that had been paired with a neutral image during learning (or sham sounds) will be presented via loudspeaker (with a 55 dB sound pressure level). Randomly ordered sounds will be presented with an interstimulus interval of 6 seconds with a random jitter of 0 to 0.4 seconds. Each of the sounds will be cued a maximum of 12 times. A trained research assistant will inspect the EEG in real time to determine sleep states and to detect any indicator of an arousal, while an AASM certified sleep technologist will supervise weekly and review all records. Cueing will begin when a participant has spent more than 10 minutes in NREM stage N3 sleep and will be immediately stopped whenever any sign of an arousal, waking up, or any other change in sleep states is observed by the experimenter. In line with prior work

showing beneficial effects of cueing of emotional stimuli during NREM but not REM sleep, and our focus on peripuberty as a developmental cusp of dynamic changes in related neuromaturational processes, we focus only on NREM reactivation in this study

Polysomnography data acquisition parameters. Participants in the sleep condition will be wired for polysomnography following the Study session using Alice Respironic Sleepware G3 or Natus SleepWorks System. The LD_E Headbox EEG will be placed on the scalp for recording of electroencephalographic (EEG) signals (i.e., C3, C4, F3, F4, O1, O2, FCZ, FZ, each referenced to linked mastoids A1/A2) in combination with two electrooculographic (EOG) and two electromyographic (EMG) leads. Signals will be sampled at 500 Hz. These procedures allow for sleep staging according to standard criteria. Quantitative EEG (qEEG) will also be calculated using our team's established methods. Briefly, artifacts will be rejected in 4-second epochs using an automated algorithm for EMG-twitches, and manually to remove eye-movement and pulse artifacts. Artifact-free NREM and REM epochs will be subjected to spectral analysis using a fast Fourier transform model.

MRI acquisition and preprocessing parameters (NOT relevant for clinical trial outcomes but included here for procedural reference). Neuroimaging data will be collected on a Siemens Prisma 3T scanner equipped with a 32-channel head coil at Florida International University. BOLD (TR/TE = 2000/25 ms, flip angle = 75°, resolution = 2.5 x 2.5 x 3 mm, FOV = 240 x 240 mm², 42 axial slices) and structural (T1-weighted magnetization-prepared rapid gradient-echo [MP RAGE], TR/TE = 9.184/3.68 ms, flip angle = 90°, resolution = 1 x 1 x 1 mm, and FOV = 256 x 256 mm) MRI data will be collected during the Study session and Test session following a 1-week delay. Neuroimaging data will be preprocessed and analyzed using Nipype⁹⁹ and standard preprocessing pipelines from Nipy¹⁰⁰, artifact detection toolbox (ART – as implemented in Nipype) and custom in-house software. Briefly, the following preprocessing steps will be implemented: simultaneous slice-timing and motion correction¹⁰⁵, registered to structural scans, normalized to a study specific template, temporally high-pass filtered (0.008 Hz) and spatially smoothed with a 5 mm FWHM Gaussian kernel. Data will be reviewed for motion related artifacts. Data points (TRs) that exceed 3 z-normalized standard deviations away from the global brain activation or a composite frame-wise displacement of 0.5 mm from the preceding scan will be flagged as outliers. Motion parameters and their first and second derivatives as well as outlier time points will be regressed out of the first level general linear models. The amygdala and subfields of the hippocampus will be automatically segmented using a multi-atlas segmentation, similarity-weighted voting, and learning-based bias correction technique implemented in the Advanced Normalization Tools (ANTs) package. Automatic segmentation will be followed by manual verification and corrections.

Statistical Plan

Primary Hypothesis (1 week outcomes): We expect audio cueing of neutral memories relative to sham cueing will result in decreased Lure Generalization Index (LGI) for negative stimuli and increased LGI for neutral stimuli at one week. To test these hypotheses, we will employ a mixed-effects model. The dependent variable will be the Lure Generalization Index (LGI) at 12 hours. The model will include fixed effects for valence (neutral vs. negative stimuli), experimental condition (neutral Targeted Memory Reactivation [TMR] vs. sham), and their interaction term (valence x condition). A random subject effect will be included to account for individual variability. Age (months) and gender will also be included as fixed effects to control for known gender and developmental differences in sleep, memory and anxiety. Should the valence by condition interaction prove statistically significant, we will conduct planned post-hoc comparisons (using t-tests with the Welch-Satterwaite equation) to thoroughly investigate the directionality and magnitude of the effects for LGI across the different valence categories and experimental conditions.

Secondary Hypothesis (12 hour outcomes): We will apply the same analytical approach as described for the 1-week outcomes to the 12-hour outcomes. We expect to observe a similar pattern of results, though with a smaller effect size.

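### The document does not settle whether 1 week, 12 hours or both carry the primary claim, and gives no rule for when the two disagree

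*Combined protocol and SAP*

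**What the plan says.** Four places bear on the status of the two delays.

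- **Cover letter:** "The primary outcomes for the clinical trial included memory outcomes at 1 week and 12 hours". Both delays are called primary, and the registry entry and the plan are cited as sources for that.
- **Protocol, Design section:** "Analyses will compare the effects of neutral TMR (relative to sham) on negative and neutral generalization at both the 12-hour and 1-week delay assessment points". Both delays are listed, without ranking.
- **Statistical Plan, first paragraph:** the heading opens "Primary Hypothesis (1 week outcomes", and the expected effects are stated for one week. The model that follows is then specified as: "The dependent variable will be the Lure Generalization Index (LGI) at 12 hours".
- **Statistical Plan, second paragraph:** "Secondary Hypothesis (12 hour outcomes): We will apply the same analytical approach as described for the 1-week outcomes to the 12-hour outcomes". A smaller effect is expected at this delay, with no figure given.

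The only testing rule is: "Should the valence by condition interaction prove statistically significant, we will conduct planned post-hoc comparisons". It operates within one delay. The document gives no significance level, testing order, multiplicity adjustment or definition of success across the two delays.

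**The concern.** The letter points to the plan for two primary outcomes, and the plan does not contain two. It ranks the delays by heading, and then names the lower-ranked delay in the model for the higher-ranked one. A reader cannot tell from this document which test decides the trial.

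The two delays answer different questions: generalization on the morning after cueing, and whether an effect is present about a week later. The sponsor expects a smaller effect at 12 hours and there are 30 children per arm, so discordant results are quite possible. Suppose 12 hours is positive and 1 week is null. Under the plan's headings the primary objective is missed. Under the letter, one of two primary outcomes is positive, and nothing says whether that is enough. The same data could be reported as a success or as a failure.

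**Working it through.** **Step 1. The texts side by side.**

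| Place | 1 week | 12 hours |
|---|---|---|
| Cover letter | primary | primary |
| Design section | listed, unranked | listed, unranked |
| Statistical Plan, headings | primary hypothesis | secondary hypothesis |
| Statistical Plan, model under the 1-week heading | not named as dependent variable | dependent variable |

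These are all current text; none comes from an amendment log. The letter and the plan's headings disagree about 12 hours. The plan's primary heading and its own model disagree about which delay is analysed. Correcting the model line alone would leave the letter in conflict with the headings. Correcting the letter alone would leave the primary model on 12-hour data.

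**Step 2. Size of the consequence.** The document has no error rate or power figure to reproduce. Inputs:

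- number of delays: 2 (document);
- two-sided level per delay: 5% (assumed, none stated);
- correlation ρ between the two interaction test statistics: 0 to 0.9 (assumed, none stated; the same children do the task at both delays, so high values should be shown).

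If either delay alone counts as success and there is no true effect at either:

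- Independent tests: 1 − (1 − 0.05)² = 1 − 0.9025 = 0.0975.
- Correlated tests: 1 − P(|Z₁| ≤ 1.96 and |Z₂| ≤ 1.96), with Z₁ and Z₂ bivariate normal with correlation ρ.

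| ρ | Chance of at least one false positive |
|---|---|
| 0 | 9.75% |
| 0.3 | 9.5% |
| 0.5 | 9.1% |
| 0.7 | 8.3% |
| 0.9 | 7.0% |

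Other rules at the same assumed level:

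- One named primary delay: 5%.
- Both delays required: at most 5%, since a false claim needs a false positive at whichever delay has no effect.
- Both primary with an equal split at 2.5% each: at most 5%; for independent tests, 1 − (1 − 0.025)² = 0.0494.

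**Step 3. What a stricter threshold would cost.** With one LGI value per child per valence, the valence-by-condition test amounts to comparing the negative-minus-neutral difference between two groups of 30. Assuming 80% power and a normal approximation, the detectable difference, in SDs of that within-child difference, is (z for the level + 0.842) × √(2/30), where √(2/30) = 0.258:

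- at 5%: (1.960 + 0.842) × 0.258 = 0.72;
- at 2.5%: (2.241 + 0.842) × 0.258 = 0.80.

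**The case against.** The strongest reply is that a transmittal letter sets no analysis. It stands ahead of the protocol, is written in the past tense, and summarises what is held elsewhere. The Statistical Plan has explicit primary and secondary headings, and a reader who follows them would take 1 week as primary. One can add that outcomes and hypotheses are different things: two outcome measures may both be registered as primary while the hypotheses about them are ranked. The 12-hour dependent variable also looks like a drafting slip, because the second paragraph refers back to an approach described for 1 week.

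Part of this stands. The conflict is one of labelling, and the plan's headings do favour 1 week. But the letter states what the primary outcomes are and cites the plan as a source, so it cannot be set aside as speaking of something else. The plan is also not a clean hierarchy to fall back on while its primary model names the other delay.

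A reader might infer that simply keeping the plan and amending the letter is enough. The documents do not support that. The letter also cites the registry entry, which is not available here. If that entry lists both delays as primary, the amendment would demote a registered primary outcome, and the letter, dated July 2025, says individual data are already available.

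**Conclusion.** The point holds as an inconsistency between current parts of the document. The delay that carries the primary claim is not fixed, and no rule covers a discordant result.

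A reader might go further and infer that the trial's false-positive rate is nearly 10%, or that a positive 12-hour result alone already counts as primary success. Neither is established. The letter calls both delays primary but does not say that one is enough, and it does not exclude requiring both. The range of 7.0% to 9.8% applies only if either delay alone suffices, each is tested at an assumed two-sided 5%, and the assumed correlation lies between 0.9 and 0. If both delays are required, the error rate is at most 5%.

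This should be corrected. The data and the form of the model do not change, but what the trial may conclude does.

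**What to change.** Reconcile the cover letter and the Statistical Plan against the earliest dated prespecified record (registry entry or grant plan), not against the results. Date the correction and name the record used. State the significance level. Then adopt whichever branch that record supports:

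- **1 week is the sole primary.** Correct the letter. Set the dependent variable of the primary model to LGI at 1 week. Add a sentence that a 12-hour result alone is reported as secondary, whatever the 1-week result.
- **Both delays are primary.** Relabel the second paragraph of the Statistical Plan and write out a separate model for each delay. Test the two valence-by-condition interactions with Holm's procedure at an overall two-sided 5%: the smaller p-value against 2.5% and, if that passes, the larger against 5%.

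No new data are needed. Under the first branch, a lone 12-hour result can no longer be claimed as primary success. Under the second, the smaller p-value faces a stricter threshold; for a test held to 2.5%, the detectable difference rises from about 0.72 to 0.80 SD under the assumptions above. If the record shows both delays as primary, moving to the first branch now would be a change after data collection and would have to be declared as such.

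### Allocation precedes the N3 threshold for cueing, so any TMR child who never reaches it attenuates the contrast; opening the allocation at the threshold is a cheap improvement

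*Combined protocol and SAP*

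**What the plan says.** - **When allocation happens (Design).** "Following PSG setup, participants will be randomly assigned to either the TMR (n=30) or sham reactivation (n=30) group". This is done by an independent assistant in a control room, before any sleep is recorded that night.
- **When sound starts and stops (Sleep Experimental Protocol).** "Cueing will begin when a participant has spent more than 10 minutes in NREM stage N3 sleep". Cueing "will be immediately stopped whenever any sign of an arousal, waking up, or any other change in sleep states is observed by the experimenter". The same rules apply to sham sounds.
- **How much cueing (same section).** "Each of the sounds will be cued a maximum of 12 times". A maximum is given, but no minimum.
- **What is compared (Statistical Plan).** The fixed effects include "experimental condition (neutral Targeted Memory Reactivation [TMR] vs. sham), and their interaction term (valence x condition"). No analysis set and no variable for cues received is defined.
- **Sample size (Participants).** "A total of 60 children between the ages of 10 and 13 years will participate in Aim 3". No effect size, SD, alpha or power accompanies it.

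The documents do not say what happens to a child who never reaches the N3 threshold: no repeat night, replacement, minimum exposure or sensitivity analysis is described. On blinding, the Design section names the participants and the assistant who deals with them directly. It does not say whether the person reading the EEG knows the arm.

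**The concern.** Between allocation and the first cue there is a condition that a child may fail. These are anxious 10- to 13-year-olds sleeping in a hospital laboratory, wired for PSG, after an MRI session, and no laboratory adaptation night is described. The 7-10 day sleep assessment is done at home, so it cannot show who will fail to reach N3 in the laboratory.

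A TMR child who fails the condition has no reactivation, yet enters the model as TMR. The question of Aim 3 is mechanistic: whether cueing neutral memories displaces negative ones. Children without cues carry no information about that, and with 30 per arm there is little power to spare.

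The order also matters for blinding. If whoever judges N3 knows the arm, that judgement could differ between arms. The documents do not exclude this.

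**Working it through.** **What can be reproduced.** Only 30 + 30 = 60. The plan gives no power calculation, so the figures below illustrate the size of the effect and do not check a stated number.

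**Inputs**
- From the documents: n = 30 per arm; outcome LGI; valence-by-condition interaction.
- Assumed: two-sided alpha 0.05; no dropout; an effect d that gives exactly 80% power when every child is cued; a share f of children in each arm never reaching the threshold, shown at 2%, 5%, 10% and 20%.

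**Set-up.** With two valences per child, the interaction is a two-group comparison of each child's negative-minus-neutral LGI difference. For a two-sample t-test with 30 per arm, 80% power needs d = 0.736 (a normal approximation gives 0.72, and powers within about a point).

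**Formulas**
- Uncued children kept: the expected effect becomes d(1 − f), with 30 per arm. A simulation confirmed the factor: at f = 10% and d = 0.723 the mean difference was 0.652, against 0.651 expected.
- Equivalent sample: 60(1 − f)². At f = 10%, 60 × 0.81 = 48.6.
- Allocation opened at the threshold, 60 children brought to the lab, no replacement: effect d, with 30(1 − f) per arm.
- Children needed in the lab to randomise 60: 60/(1 − f). At f = 20%, 60/0.80 = 75.

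| Uncued share f | Diluted effect | Power, all kept | Equivalent sample | Power, later allocation, no replacement | Lab children needed to randomise 60 |
|---|---|---|---|---|---|
| 0% | 0.736 | 80% | 60 | 80% | 60 |
| 2% | 0.721 | 78% | 57.6 | 79% | about 61 |
| 5% | 0.699 | 76% | 54.2 | 78% | about 63 |
| 10% | 0.662 | 71% | 48.6 | 76% | about 67 |
| 20% | 0.588 | 61% | 38.4 | 70% | 75 |

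With replacement up to 60 randomised, power returns to 80% in every row. Mixing cued and uncued children also widens the spread in the TMR arm, which takes roughly a further 0.5 to 2 points off the third column for shares of 5% and above.

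**How likely is any uncued child?** At f = 5%, 30 × 0.05 = 1.5 are expected per arm, and the chance of at least one among 60 is 1 − 0.95^60 = 95%.

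**Which arm causes the loss.** The factor (1 − f) comes from the TMR arm. An uncued sham child misses guitar strums; if those do not affect memory, the contrast does not shrink on that child's account.

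**The case against.** **The size is unknown and may be small.** This stands. No uncued rate is given, and at 2% the loss is under 2 points. The plan also evaluates sleep disorders, takes a history of medication affecting sleep, and aligns laboratory timing with sleep at home, all of which may keep the rate down.

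**Analysing everyone as randomised is legitimate.** This stands. It answers a question about assignment to cueing and is valid under the null. A reader might infer that the planned comparison is biased towards finding an effect; the documents do not support that.

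**Leaving out uncued children need not break the randomisation.** A reader might infer that it must. But no sound is played before the threshold, so cues cannot influence who reaches it. Restricting both arms to those who did is a fair comparison if N3 staging is blind to arm. What the documents lack is that assurance, and a plan for such an analysis.

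**Later allocation does not by itself restore power.** This stands. Without replacement its power equals that of the restricted analysis under the present timing; the return to 80% comes from recruiting more children. Each non-qualifier will have been through intake, home monitoring, MRI encoding and PSG set-up.

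**The remedy is partial.** This stands too: children who start cueing but receive few cues remain.

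**It may be too late.** The covering letter of July 2025 says that individual data are already available in an archive, which suggests that randomisation is over. Only the analysis-stage remedy would then be usable.

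**Conclusion.** The point holds as an avoidable loss of power, and as a gap in how uncued children are handled. Under the assumptions above, keeping 2% to 20% uncued children lowers power from 80% to between 78% and 61%. Opening the allocation at the threshold gives 79% to 70% from the same 60 laboratory children, and 80% only with about 61 to 75 children brought in. Even without replacement, its power is no worse than that of the present order.

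A reader might infer that uncued children dilute the result equally from both arms, or that many are to be expected. Neither follows: the attenuation comes mainly from the TMR arm, and the rate is not in the documents. The gain that does not depend on the rate is that the N3 judgement would be made before the arm is known, which the documents do not otherwise guarantee. This is a cheap improvement, not a flaw that invalidates the trial.

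**What to change.** **If randomisation is still open.** In the Design section, replace the timing after PSG set-up with wording such as: *The independent control-room assistant opens the allocation only when the existing N3 criterion for cueing has been met. Children who never meet it are recorded as not randomised.* The cueing criterion itself is unchanged. State whether non-qualifiers are replaced to reach 60 randomised.

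**If randomisation is complete.** Report the all-randomised analysis, and beside it an analysis of children in both arms who met the criterion. State whether the person staging N3 was blind to arm; the second analysis is a fair comparison only if so.

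**In either case.** Report the number of children who were never cued and, for those randomised, the cues delivered by arm, since neither remedy deals with children who received few.

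**Cost.** A wording change, no new staff role, and an allocation that must be opened during the night just as cueing is due. The result then applies to children who reach the criterion. Replacement, if chosen, costs about 1, 3, 7 or 15 extra children through the laboratory at uncued shares of 2%, 5%, 10% or 20%.

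### The primary (1-week) analysis names LGI at 12 hours as its outcome, so the plan as written models 12 hours twice and 1 week not at all

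*Combined protocol and SAP*

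**What the plan says.** All of the analysis text is in two paragraphs of the Statistical Plan.

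- The first is headed "Primary Hypothesis (1 week outcomes" and predicts "decreased Lure Generalization Index (LGI) for negative stimuli and increased LGI for neutral stimuli at one week".
- It introduces a mixed-effects model to test that prediction and defines its outcome: "The dependent variable will be the Lure Generalization Index (LGI) at 12 hours". The fixed effects are valence, condition, their interaction, age and gender, with a random subject effect. There is no term for time.
- The second paragraph, on the secondary hypothesis, says: "We will apply the same analytical approach as described for the 1-week outcomes to the 12-hour outcomes". It expects the same pattern with a smaller effect.

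Two other places bear on the point. The Design section says the comparison will cover "negative and neutral generalization at both the 12-hour and 1-week delay assessment points". The cover letter states: "The primary outcomes for the clinical trial included memory outcomes at 1 week and 12 hours".

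**The concern.** The primary hypothesis is about one week, but the model offered to test it is fitted to the 12-hour data. Because the secondary analysis is also at 12 hours, a literal reading gives two analyses of the same endpoint and none of the primary one.

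Two things are at stake. First, the primary hypothesis would be judged on the wrong endpoint, and on the one the plan has reason to regard as weaker: fewer lures are tested and a smaller effect is expected. Second, the cover letter is dated July 2025 and says individual data are already available. A plan that can be read either way leaves room to pick the time point after the results are known. That is a risk created by the text; nothing in the documents shows that it happened.

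**Working it through.** **1. The text side by side**

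| Place | Time point |
|---|---|
| Statistical Plan, heading of primary paragraph | 1 week |
| Statistical Plan, primary hypothesis | 1 week |
| Statistical Plan, outcome of the primary model | 12 hours |
| Statistical Plan, secondary analysis | 12 hours |
| Design, planned comparisons | both |
| Cover letter, primary outcomes | both |

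Only one sentence in the Statistical Plan names a dependent variable, and it says 12 hours. As the model has no time term, the 1-week data cannot enter it by another route. Literal count of models specified: two at 12 hours, none at 1 week.

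**2. Whether the time point matters: the item counts**

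The Emotional Memory Task Protocol section gives, for 12 hours, a set of 16 study images that "will be tested at the 12-hour Test session along with 30 lures (15 neg) and 24 foils (12 neg". For the later session, "44 study images (22 neg) will be tested at the 1-week Test session with 85 lures (43 neg". So there are 15 negative and 30 − 15 = 15 neutral lures at 12 hours, and 43 negative and 85 − 43 = 42 neutral lures at 1 week. The totals agree with the plan: 16 + 30 + 24 = 70, 44 + 85 + 67 = 196, and 70 + 196 = 266, the stated number of test images.

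The documents give no formula for LGI, so I use the proportion of lures called old as a stand-in. For one child, the item-sampling SD of the negative-minus-neutral difference is √[p(1−p)(1/n_neg + 1/n_neu)]. With an assumed rate p = 0.40, p(1−p) = 0.24:

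- 12 hours: √[0.24 × (1/15 + 1/15)] = √0.0320 = 0.179
- 1 week: √[0.24 × (1/43 + 1/42)] = √0.0113 = 0.106

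The variance ratio is 0.0320/0.0113 = 2.83. When p is the same for both valences and both sessions it cancels, so the ratio depends only on the lure counts. The SDs themselves run from 0.146 to 0.183 at 12 hours and from 0.087 to 0.108 at 1 week for p from 0.2 to 0.5.

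**3. Illustration of power for the valence-by-condition interaction**

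From the Design section: 30 per arm. Assumed, because the documents give none of these: two-sided α = 0.05; an interaction of 0.15 at 1 week and two-thirds of that, 0.10, at 12 hours; and a between-child SD of the true difference, τ, of 0.10, 0.15 or 0.20. The total SD is √(τ² + item variance). The noncentrality is effect/(SD × √(2/30)), on 58 degrees of freedom.

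| τ | SD, 1 week | SD, 12 h | Power, 1 week (0.15) | Power, 12 h (0.10) | Power, 12 h (0.15) |
|---|---|---|---|---|---|
| 0.10 | 0.146 | 0.205 | 97% | 46% | 80% |
| 0.15 | 0.184 | 0.233 | 87% | 37% | 69% |
| 0.20 | 0.226 | 0.268 | 71% | 29% | 57% |

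The last column keeps the effect at 0.15 to separate the two causes. Fewer lures alone cost about 14 to 19 percentage points; the rest of the gap comes from the assumed smaller effect. The ratio of total variances, 12 hours to 1 week, is 1.97, 1.61 and 1.40 for the three values of τ, well below the 2.83 for item noise alone.

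**The case against.** The best reply is that this is an evident slip and that the plan as a whole does commit to a 1-week analysis. The heading and the hypothesis both say one week, the secondary paragraph refers back to the model as the one for the 1-week outcomes, and the Design section promises both time points. That is a fair account of what was probably meant. It does not repair the text: the sentence that fixes the outcome variable says otherwise, and no other sentence in the Statistical Plan overrides it.

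A second reply is that the freedom to choose a time point does not come from this phrase alone, because the cover letter already calls both time points primary. That stands. It is a separate inconsistency in the endpoint hierarchy, and correcting the phrase would not remove it. It also makes the slip harder to set aside, since a 12-hour primary result could not be dismissed as plainly outside the plan.

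Third, the power figures rest on assumptions. The lure rate, the effects, the two-thirds ratio and the between-child SDs are not in the documents, and an LGI corrected for foil or target responses would have different noise. This too stands. The figures show what using the 12-hour data could cost. The contradiction does not depend on them.

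**Conclusion.** The concern holds. Followed as written, the Statistical Plan specifies no model for its primary outcome and specifies the 12-hour model twice. This rests on the text alone and needs no assumption. The conclusion is about the wording; it does not imply that the sponsor meant to leave out the 1-week test.

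The size of the consequence is less certain. The 2.8-fold difference in item variance follows from the lure counts, if LGI behaves like a simple lure rate that is equal across valences and sessions. The drop in power from 71–97% to 29–46% is an illustration that further depends on the assumed effects and between-child SDs. Correction is required because the phrase defines the primary outcome variable.

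**What to change.** In the primary paragraph of the Statistical Plan, state that the dependent variable is LGI at 1 week. In the secondary paragraph, state that the identical model is fitted with LGI at 12 hours as the dependent variable. In the same revision, bring the cover letter and the Statistical Plan into agreement on whether 12 hours is primary or secondary, and record which time point was used in any primary analysis already run.

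The cost is a one-phrase correction and a clarifying sentence or two. No new data or procedures are needed.
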